2.2. Background

2.3. Overactive Bladder in Men with Benign Prostatic Hyperplasia

OAB is highly prevalent and affects approximately 16% of the population in the United States and Europe. Prevalence increases with age, affecting approximately a third of people 75 years and older [Stewart, 2003; Milsom, 2001]. Despite similar prevalence between the sexes and growing clinical trial evidence that men benefit from pharmacotherapy, men are less likely to use treatment for OAB [Goldman, 2016].

The International Continence Society (ICS) defines OAB as urgency, with or without urge incontinence, usually associated with frequency and nocturia [Abrams, 2002]. Urgency is defined as a sudden compelling desire to void which is difficult to defer and, from the medical definition perspective, it is a necessary symptom for OAB. Urgency incontinence is the involuntary loss of urine accompanied by urgency (referred to as OAB Wet) and is present in approximately one-third of patients with OAB [Stewart, 2003; Milsom, 2001]. In the absence of incontinence, OAB is referred to as OAB Dry. Urgency incontinence is distinguished from stress urinary incontinence, which is the involuntary loss of urine on effort or physical exertion (eg, sporting activities), or upon sneezing or coughing. When both components are present, the classification is mixed urinary incontinence, with either urgency or stress specified as the predominant component.

Although the overall prevalence of OAB in men and women is similar, there are major differences in predominating symptoms. Men are more likely to experience urgency, frequency, and nocturia accompanied by lower urinary tract symptoms (LUTS) associated with voiding dysfunction, whereas women are twice as likely to experience incontinence [Tubaro, 2017]. Since most men with OAB symptoms do not have urinary incontinence, the micturition frequency and the urgency become the predominant symptoms that characterize the disease for the men with OAB on pharmacological therapy for BPH [Helfand, 2012]. Among men, urinary incontinence significantly increases after the age of 65 years.

Historically in men with BPH, LUTS have been presumed to result from bladder outlet obstruction secondary to prostate enlargement. However, men may have OAB symptoms in the absence of, or in conjunction with, voiding symptoms associated with BPH or urodynamic evidence of bladder outlet obstruction [Nakagawa, 2008; Hyman, 2001]. BPH can be associated with debilitating LUTS, categorized by storage symptoms (eg, urinary frequency, urgency, and nocturia) and voiding dysfunction (eg, decreased and intermittent force of stream and the sensation of incomplete bladder emptying).

2.3.1. Vibegron

Initial pharmacologic therapy for OAB symptoms in men with BPH traditionally has been directed at minimizing the obstruction, and has included α 1-adrenergic receptor antagonists to relax the muscles of the prostate and bladder neck or 5-ARIs to reduce prostate growth [American Urological Association, 2010]. While patients may see some improvement in OAB symptoms with these BPH therapies (eg, improvement in urinary flow), symptom control for OAB symptoms is incomplete, for many, and urinary urgency, incontinence, frequency, or nocturia persists [Abrams, 2002]. To address persistent OAB symptoms in men with BPH, combinations of BPH therapies with OAB medications, such as anticholinergics, have shown promise [Chapple, 2009; Oelke, 2008]. However, the clinical use of anticholinergics is limited by mechanism-based side effects including dry mouth and constipation [MacDiarmid, 2008] and the potential for CNS adverse effects [Gray, 2015; Risacher, 2016]. Further, contraindications/precautions exist due to the possibility of urinary retention and bladder outflow obstruction [Detrol prescribing information, 2016].

β 3-adrenoceptor (β 3-AR) agonists for OAB (eg, mirabegron) have demonstrated efficacy in treating persistent OAB symptoms in men on BPH therapies [Ichihara, 2014] with a more favorable safety profile relative to the anticholinergics. In fact, experts have recommended that these agents be specifically studied in this patient population [Maman, 2014; Chapple, 2009; Van Kerrebroeck, 2001; Chapple, 2017].

Vibegron is a potent and highly selective β 3-AR agonist demonstrating > 9000 -fold selectivity for activation of β 3-AR over β 2-AR and β 1-AR in cell based in vitro assays. β -adrenergic receptors are prototypic G-protein coupled receptors expressed on the surface of cells, and mediate intracellular signaling via coupling to G_s and increasing levels of intracellular cyclic

adenosine monophosphate (cAMP). β_3 -ARs are widely distributed in humans and are the most prevalent β -AR subtype expressed on human detrusor smooth muscle [Takeda, 2000]. In isolated human bladder smooth muscle, activation of β_3 -AR using subtype-selective agonists results in smooth muscle relaxation suggesting a role for β_3 -AR agonists during the filling phase of the micturition cycle [Yamaguchi, 2002; Biers, 2006]. In rodent models of bladder over activity, β_3 -AR agonists relax bladder smooth muscle and suppress detrusor smooth muscle instability and hyperreflexia [Takeda, 2000; Woods, 2001; Takeda, 2002; Kaidoh, 2002]. In rhesus monkeys, dose-dependent increases in bladder capacity and decreases in micturition pressure were observed with vibegron. Bladder capacity was further increased by vibegron in combination with tolterodine or darifenacin [Di Salvo, 2017]. These results have supported a large and comprehensive clinical development program for vibegron in the general OAB population, including both male and female subjects.

More than 2300 subjects (including 1840 with OAB and 460 healthy volunteers) have received vibegron in Phase 1, 2, and 3 clinical studies. Assessment of safety laboratory parameters and mean vital sign values over time, including heart rate and blood pressure, showed no clinically meaningful differences for any active treatment group relative to placebo or anti-muscarinic comparators. A large, multicenter Phase 3 study of vibegron for the treatment of OAB in women and men is ongoing. Discontinuation rates due to adverse events (AEs) were low (< 5%) in all clinical studies conducted to date with vibegron. In a completed Phase 3 study in Japan in more than 1200 subjects with symptoms of OAB, there were no notable mean changes in post-voided residuals observed [Yoshida, 2018]. A more detailed description of vibegron, including pharmacology, efficacy, and safety data in overactive bladder, is provided in the Investigator's Brochure.

2.4. Benefit/Risk Assessment

2.4.1. Potential Benefits

Vibegron's mechanism of action has the potential to demonstrate significant therapeutic benefit in the treatment of OAB symptoms in men with BPH on pharmacological therapy for their BPH symptoms.

2.4.2. Potential Risks

The initial clinical program for vibegron in the treatment of OAB included subjects of both sexes. The Phase 3 program in OAB (RVT-901-3003 and RVT-901-3004) included approximately 15% males, contributing safety data comprising 217 men in addition to those enrolled in Study URO-901-3005. More detailed information about the known and expected benefits and risks from the study and reasonably expected AEs of vibegron may be found in the Investigator's Brochure.

Based on aggregate preclinical, clinical pharmacology, and Phase 2 and 3 studies, AEs of special interest (AESIs) were predefined for specific evaluations in vibegron clinical studies as follows:

- Potential major cardiovascular events
- Hypertension
- AEs suggestive of orthostatic hypotension
- AEs suggestive of cystitis or urinary tract infection
- Elevated aspartate transaminase (AST) or alanine transaminase (ALT) laboratory value requiring that the study drug be temporarily withheld or permanently discontinued
- Neoplasm

In addition, the risk for increases in post void residual urine volume and urinary volume will be closely monitored for post-void retention during the study. The study's enrollment criteria will exclude men with PVR volume ≥ 100 mL at screening and at baseline and those with maximum urinary flow (Qmax) less than 5 mL/second. Post-void residual urine volume will be assessed throughout the study, and subjects with a single PVR volume of ≥ 300 mL or an AE of urinary retention will be withdrawn.

Prespecified definitions of urinary retention and other AESIs are provided in the Adverse Event of Special Interest section ([Section 8.4.6](#)).

3. Objectives and Endpoints

Objectives	Endpoints
Primary Efficacy 
 To assess the efficacy of vibegron compared with placebo in men with OAB symptoms on pharmacological therapy for BPH as defined by micturition and urgency episodes 	Primary Efficacy 
 CFB at Week 12 in the average number of micturition episodes per day CFB at Week 12 in the average number of urgency episodes (urgency: need to urinate immediately) per day
Secondary Efficacy 
 To assess the efficacy of vibegron compared with placebo in men with OAB symptoms on pharmacological therapy for BPH as defined by other key measures 	Secondary Efficacy 
 CFB at Week 12 in the average number of nocturia episodes per night CFB at Week 12 in the average number of urge urinary incontinence episodes per day for subjects with urinary incontinence at baseline CFB at Week 12 in the IPSS Storage score (1-week recall) CFB at Week 12 in the average volume voided per micturition
Safety 
 To assess the safety and tolerability of vibegron compared with placebo in men with OAB symptoms on pharmacological therapy for BPH 	Safety 
 AEs, concurrent medications, clinical laboratory, vital sign assessments, PVR volume, uroflow measures, IPSS, urodynamics (sub-study only)
Other Efficacy 	Other/Exploratory - Efficacy 
 CFB at Week 2, Week 4, Week 8, Week 16, Week 20 and Week 24 in the average number of micturition episodes per day CFB at Week 2, Week 4, Week 8, Week 16, Week 20, and Week 24 in the average number of urgency episodes per day CFB at Week 2, Week 4, Week 8, Week 16, Week 20 and Week 24 in the average number of nocturia episodes per night CFB at Week 4, Week 8, Week 20, and Week 24 in the IPSS Storage score (1-week recall) CFB at Week 4, Week 8, Week 12, Week 20, and Week 24 in the IPSS Quality of Life score (1-week recall) CFB at Week 4, Week 8, Week 12, Week 20, and Week 24 in the IPSS Voiding score (1-week recall) CFB at Week 2, Week 4, Week 8, Week 16, Week 20, and Week 24 in the average number of urge urinary incontinence episodes per day for subjects with urinary incontinence at baseline CFB at Week 2, Week 4, Week 8, Week 16, Week 20, and Week 24 in the average volume voided per micturition CFB at Week 2, Week 4, Week 8, Week 12, Week 16, Week 20, and Week 24 in the average number of total incontinence episodes per day for subjects with urinary incontinence at baseline

- Percent of all subjects with a 50% reduction from baseline in average urgency episodes (urgency: need to urinate immediately) per day at Week 2, Week 4, Week 8, Week 12, Week 16, Week 20, and Week 24
- Percent of subjects with urinary incontinence at baseline with a 75% reduction from baseline in average urge urinary incontinence episodes per day at Week 2, Week 4, Week 8, Week 12, Week 16, Week 20, and Week 24

Other/Exploratory - Quality-of-Life

- CFB at Week 12 in Symptom Bother Score as assessed by [REDACTED], 1-week recall)
- CFB at Week 12 in HRQL total score as assessed by [REDACTED] (HRQL includes subscales: coping, concern, sleep and social interaction. The total score will be calculated by adding the 4 subscales scores.)
- CFB at Week 12 and Week 24 in HRQL subscale Coping score as assessed by [REDACTED]
- CFB at Week 12 and Week 24 in HRQL subscale Concern score as assessed by [REDACTED]
- CFB at Week 12 and Week 24 in HRQL subscale Sleep score as assessed by [REDACTED]
- CFB at Week 12 and Week 24 in HRQL subscale Social Interaction score as assessed by [REDACTED]
- CFB at Week 12 and Week 24 in [REDACTED] as assessed by measure of health status questionnaire developed by the EuroQoLGroup
- CFB at Week 4, Week 12, and Week 24 in overall bladder symptoms based on [REDACTED]
- CFB at Week 4, Week 12, and Week 24 in overall control over bladder symptoms based on [REDACTED]
- CFB at Week 4, Week 12, and Week 24 in overall symptom frequency based on [REDACTED]
- CFB at Week 4, Week 12, and Week 24 in overall urgency-related leakage over bladder symptoms based on [REDACTED] in subjects with urinary incontinence at baseline
- Overall change of bladder symptoms based on [REDACTED] at Week 4, Week 12, and Week 24
- CFB at Week 12 and Week 24 in the [REDACTED]

Note: "per day" refers to a continuous 24-hour period.

Abbreviations: AE = adverse events; BPH = benign prostatic hypertrophy; CFB = change from baseline; HRQL = health-related quality of life; [REDACTED] IPSS = International Prostate Symptom Score; OAB = overactive bladder; [REDACTED] PGI = Patient Global Impression; QoL = quality of life; PVR = post-void residual

4. Study Design

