5.1. Inclusion Criteria

At the **Visit 1 (Screening)** visit (and other timepoints as noted), a subject will be eligible for inclusion in this study only if all of the following criteria apply, unless otherwise noted:

1. Capable of giving written informed consent, which includes compliance with the requirements and restrictions listed in the consent form.
2. Male subjects of 45 years of age and above.
3. Body weight ≥ 50 kg (inclusive).
4. Subject should have been on and agree to continue to stay on a stable dose of BPH treatment with either a) alpha blocker monotherapy or b) alpha blocker + 5 ARI. Subjects on alpha blockers should have started their therapy at least 3 months prior to screening and be on a stable dose at the start of screening. Subjects on a 5-ARI should have started therapy at least 6 months prior to screening and be on a stable dose at screening.
5. Has a history of overactive bladder symptoms (frequency of ≥ 8 micturition episodes per day and urgency episodes of ≥ 3 per day with or without incontinence) while taking pharmacological therapy for at least 2 months to treat LUTS due to BPH.
6. Subject has an IPSS total score of ≥ 8 at Screening and Visit 3 (Baseline).
7. Subject has a prostate-specific antigen (PSA) level < 4 ng/mL, or if ≥ 4 ng/mL but ≤ 10 ng/mL, prostate cancer has been ruled out to the satisfaction of the investigator.
8. Subjects agrees to not participate in another interventional drug or device clinical trial during the study.
9. In the opinion of the investigator, is able and willing to comply with the requirements of the protocol, including completing study questionnaires and the Bladder Diary.
10. At Visit 2 (Run-in) and Visit 3 (Baseline) visits, subject must have both additional qualifications based on the 3-day Bladder Diary period: a) having an average of ≥ 8 but ≤ 20 micturition episodes per day over the 3-day diary period, and (b) having an average of ≥ 3 urgency episodes per day over the 3-day diary period.
11. Subject must have a post void residual (PVR) volume value of < 100 mL at Screening, Visit 2 (Run-In) and Visit 3 (Baseline).

12. At Visit 2 (Run-in) and Visit 3 (Baseline) visits, having at least 2 average nocturia episodes per night based on 3-day Bladder Diary at baseline. Nocturia is defined as waking to pass urine during the main sleep period.

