8.3.1. Vital Signs

Vital signs, including blood pressure, heart rate (by pulse), body temperature, respiration rate, weight, and height, will be assessed at the timepoints specified in the Schedule of Assessments ([Section 1.3](#) and [Section 1.4](#)) and in [Section 10.7](#) as follows:

- Blood pressure and pulse will be measured after the subject has been resting in a seated position for 5 minutes, after PRO assessments and before blood draws. Note additional requirements on timing for blood pressure assessments for visits with orthostatic assessments in Part 1 ([Section 8.3.2](#)).
- Blood pressure measurements will be taken on the same arm and by the same site staff throughout the study, if possible.
- Sitting systolic and diastolic blood pressures will be determined by averaging 3 replicate measurements obtained approximately 1 to 2 minutes apart. The average of the 3 measurements will be used for eligibility and safety assessments.
- The same method for assessing temperature should be used at all visits for a particular subject.

- Body weight will be measured with subjects in street clothing with jacket/coat and shoes removed, using the same scale throughout the study, if possible.
- Standing height will be measured without shoes at Screening only.

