9.4.3. Safety Analyses

The safety analysis will be performed using the Safety Analysis Set and will be fully defined in the SAP. The safety parameters will include AEs and clinical laboratory and vital sign, parameters. For each safety parameter of the clinical laboratory and vital sign parameters, the last nonmissing safety assessment before the first dose of study drug will be used as the baseline for all analyses of that safety parameter.

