4.3.4. Baseline and Change from Baseline

In general, the last recorded value on or prior to the date of randomization will serve as the baseline measurement for efficacy endpoints while the last recorded value prior to first double-blind dose of study treatment will serve as the baseline measurement for safety endpoints. The mean of multiple values will be used as baseline for the following situations:

- If multiple measurements are scheduled on the same baseline day (i.e., blood pressure)
- If multiple measurements are collected on the same baseline day without the time or “repeat” status to differentiate the records

For efficacy endpoints derived from the Bladder Diary, the baseline will be the average value over the diary days in the baseline analysis visit window.

Change from baseline will be calculated as the post-baseline value minus the baseline value. Percentage change from baseline will be calculated as the change from baseline divided by the baseline value, multiplied by 100. If either the baseline or post-baseline value is missing, then change from baseline and percentage change from baseline will be set to missing.

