All continuous laboratory parameters will be summarized descriptively by absolute value at each visit by treatment group, together with the corresponding changes from baseline. All parameters will be summarized in SI units.

The number and percentage of subjects with laboratory measurements outside of the central laboratory normal range will also be summarized by treatment group and visit. Shift tables from baseline to maximum post-baseline value, to minimum post-baseline value, last post-baseline value, and at each post-baseline visit will be provided for hematology and chemistry parameters to display low, normal, high, and missing values by treatment group in a 3-by-3 contingency table. Denominators for percentages will be the number of subjects with non-missing data at the specific assessment and baseline.

Maximum post-baseline total bilirubin will be presented (<2 and $\geq 2 \times$ ULN) and plotted against maximum post-baseline ALT (<3 , ≥ 3 - <5 , ≥ 5 - <10 , and $\geq 10 \times$ ULN), expressed as multiples of ULN. This will be repeated to show maximum post-baseline total bilirubin against maximum post-baseline AST.

Data for subjects with ALT or AST $\geq 3 \times$ ULN, and bilirubin $\geq 2 \times$ ULN will be presented, which will include all visits for this subset of subjects. A line plot of liver biochemistry test results (including ALP, ALT, AST, total bilirubin, and GGT) over time will also be presented for this subset of patients.

A sample for the urinalysis and urine culture will be sent to the central laboratory only if the urine dipstick performed at the site tests positive for the presence of leukocytes, nitrites, or blood cells. Dipstick results and central urinalysis data will be provided only in the listing.

Any data outside the central laboratory normal reference ranges will be explicitly noted on the listings that are produced.

7.3. **Vital Sign Assessments**

7.3.1. **Height, Weight, and Sitting Vital Signs**

Vital sign data including systolic and diastolic blood pressure, pulse rate, respiration rate, body temperature and weight will be collected at all study visits except for the safety follow-up visit. Height will be measured at Screening only. Blood pressure will be measured in triplicate at each

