visit. The average of triplicates will be used for summary; if fewer than three measurements were collected the average of available measurements will be used. For subjects in Study Part 1 and visits with orthostatic blood pressure assessments, blood pressure (in triplicate) and pulse rate taken pre-dose in sitting position are equivalent to pre-dose regular vital sign values and will be used.

Vital signs will be summarized using absolute value and change from baseline. A summary by-visit according to the visit window rule in [Section 4.2.4.2](#), the maximum, and last post-baseline observation for each subject will be summarized for each of the vital signs. For change from baseline in blood pressure and pulse rate, least squares mean estimates and 95% CIs as described in section 4.2.2 will be presented from an ANCOVA model including terms for treatment, age, baseline parameter value, and pre-existing hypertension (Yes vs. No).

The line plot of mean (SE) of change from baseline in blood pressure and pulse rate over time will be prepared. A by-subject listing, sorted by subject identifier, will be presented including all vital sign results (scheduled or unscheduled).

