7.5. Post-Void Residual (PVR) Urine Volume

PVR urine volume data will be summarized at Baseline and every visit, including change from baseline for post-baseline visits. Least squares mean estimates and 95% CIs as described in section 4.2.2 will be presented from an ANCOVA model including terms for treatment and baseline parameter value.

Categorical summaries of PVR at the following categories: < 100 mL, ≥ 100 and < 200 mL, ≥ 200 and < 300 mL, ≥ 300 mL will be presented. Line plots of least squares means change from baseline and 95% CIs by visit and treatment will be presented. All PVR data will be listed.

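### The PVR, blood pressure and pulse ANCOVAs leave out the Screening and Run-in readings; the planned intervals are valid but somewhat wider than the collected data allow

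*Protocol*

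**What the plan says.** **Three pre-dose readings.** Protocol 2.4.2 says the enrolment criteria will "exclude men with PVR volume ≥ 100 mL at screening and at baseline", which names two visits. Inclusion criterion 11 (Protocol 5.1) names three: "Subject must have a post void residual (PVR) volume value of < 100 mL at Screening, Visit 2 (Run-In) and Visit 3 (Baseline". The schedules in Protocol 1.3 and 1.4 place PVR and vital signs at all three visits in both Parts. SAP 7.3.1, in a sentence whose list opens with blood pressure and pulse, says that vital signs including "body temperature and weight will be collected at all study visits except for the safety follow-up visit".

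**One baseline.** SAP 4.3.4: "the last recorded value prior to first double-blind dose of study treatment will serve as the baseline measurement for safety endpoints". Averaging is allowed only for values from the same baseline day. Protocol 9.4.3 agrees for laboratory and vital sign parameters: "the last nonmissing safety assessment before the first dose of study drug will be used as the baseline".

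**The models.** SAP 4.2.2 fits a separate model at each timepoint. For PVR, SAP 7.5 specifies an "ANCOVA model including terms for treatment and baseline parameter value". For blood pressure and pulse, SAP 7.3.1 specifies an "ANCOVA model including terms for treatment, age, baseline parameter value, and pre-existing hypertension (Yes vs. No". Where a Baseline reading exists, no safety model uses the Screening or Run-in reading.

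**The concern.** A single-visit PVR or blood pressure is a noisy measure of a man's usual level. If his readings mix a stable level with visit-to-visit variation, the two earlier ones explain post-baseline variance that the last one misses. All three precede randomised treatment, so adjusting for them does not bias the treatment comparison.

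What is at stake is the precision of the least squares mean differences in PVR, blood pressure and pulse. Their 95% intervals show how large a mean effect can be excluded, in a population that the protocol studies partly because of possible urinary retention and in which hypertension is an event of special interest.

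**Working it through.** The documents give no standard deviation (SD), between-visit correlation, power or interval width for PVR, blood pressure or pulse, so there is no stated figure to reproduce. Every correlation below is an assumption.

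**Inputs from the documents**
- Three pre-dose visits: Protocol 1.3, 1.4 and 5.1.
- One baseline value per model: SAP 4.3.4, 7.3.1 and 7.5.
- 1:1 allocation, 544 per arm; 544 × 0.85 ≈ 462 evaluable per arm: Protocol 9.2.
- Two-sided 95% intervals: SAP 4.1.2.

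**Case 1: equal correlation r among all visits.** Per unit of outcome variance, the residual variance is 1 − r² with one reading and 1 − 3r²/(1 + 2r) with three. Interval width scales with the square root of their ratio.

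| r | One reading | Three readings | Variance ratio | Width ratio | Narrowing |
|---|---|---|---|---|---|
| 0.3 | 0.910 | 0.831 | 0.913 | 0.956 | 4% |
| 0.4 | 0.840 | 0.733 | 0.873 | 0.934 | 7% |
| 0.5 | 0.750 | 0.625 | 0.833 | 0.913 | 9% |
| 0.6 | 0.640 | 0.509 | 0.795 | 0.892 | 11% |

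Under this structure the three readings carry equal weight, so the mean of Screening and Run-in beside the last value recovers the whole gain.

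In absolute terms the half-width is 1.96 × √(2/462) × √(residual variance) = 0.129 SD × √(residual variance). At r = 0.3 it falls from 0.123 to 0.118 SD; at r = 0.5, from 0.112 to 0.102 SD.

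**Case 2: skewed, truncated PVR.** This was simulated with 544 per arm, 600 replicates and log-normal PVR (log mean 3.2, log SD 0.9, both assumed), with every pre-dose value below 100 mL as criterion 11 requires. At log-scale correlations of 0.3, 0.5 and 0.7 the width ratios with all three readings entered are 0.979, 0.953 and 0.915, a narrowing of about 2%, 5% and 8.5%. Coverage was 95.0 to 96.2% for every model, including the planned one. These correlations apply on the log scale before truncation, so they are not like for like with the table.

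**Case 3: stable level plus serial correlation plus noise.** With a stable share of 0.3 to 0.5 of the variance and a serial share of 0.2 to 0.3, the width ratios are 0.970, 0.958 and 0.937, a narrowing of about 3 to 6%.

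**Case 4: pure AR(1) decay.** The width ratio is 1.000 with all three readings entered, so there is no gain. Replacing the last value by a plain three-visit mean would give 1.01 to 1.03, slightly worse than planned.

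**Case 5: a less informative Screening reading.** Suppose Screening correlates 0.3 with everything else and the other visits correlate 0.5 with each other and with the outcome. The explained share is c′S⁻¹c.
- Readings entered separately: 0.91/2.64 = 0.345; residual 0.655; width √(0.655/0.75) = 0.935.
- Mean of Screening and Run-in plus the last value: 0.1625/0.49 = 0.332; residual 0.668; width √(0.668/0.75) = 0.944.

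**Case 6: blood pressure with its existing covariates.** If age and hypertension history already explain 10 to 20% of between-subject variance, the width ratio at r = 0.5 is 0.918 to 0.925, a narrowing of about 8% rather than 9%.

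**The case against.** **The plan is conventional and valid.** Protocol and SAP agree on the last pre-dose value, and the planned intervals are unbiased with about nominal coverage. This stands. A reader might infer that the intervals are wrong; they are not.

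**These are not the safety comparisons the trial was sized for.** A reader might infer that the trial's key safety comparisons lose precision. The documents do not support that. Neither PVR, blood pressure nor pulse has a hypothesis, margin or power, and Protocol 9.4.3.3 plans only descriptive statistics for vital signs. The safety comparisons with margins and power are urodynamic Qmax and PdetQmax (SAP 1.2.4.2). They have a single baseline assessment and are untouched.

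**The clinical harms are counted, not averaged.** A reader might infer that detection of urinary retention or hypertension suffers. It does not: those events are defined in individual men and summarised as counts and percentages. The PVR categories (SAP 7.5) and blood pressure thresholds (SAP 7.3.1.2) would not change either.

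**The blood pressure model already does more.** It includes age and pre-existing hypertension, and Protocol 8.3.1 says: "Sitting systolic and diastolic blood pressures will be determined by averaging 3 replicate measurements obtained approximately 1 to 2 minutes apart". This stands and makes the gain somewhat smaller. Replicates taken minutes apart do not remove visit-to-visit variation, so the gain need not vanish.

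**Equal correlation is optimistic.** Screening can fall up to 49 days before dosing, Protocol 8.1.3 allows washout during it, and outcomes run to Week 24. This stands, so the range has to include zero.

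**The absolute gain is small.** At r = 0.3 to 0.5 the half-width falls by 0.005 to 0.010 SD. This also stands. What remains is an improvement that uses data already collected and costs one or two degrees of freedom.

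**Conclusion.** The point holds as an optional gain in precision, not as an error. The safety ANCOVAs omit two pre-dose readings that the schedules collect. The intervals for mean change in PVR, blood pressure and pulse are therefore probably a few per cent wider than necessary: about 4 to 11% under equal correlation of 0.3 to 0.6, less under the other structures examined at similar correlations, and nothing under pure AR(1).

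These sizes rest entirely on assumed correlations. What does not depend on them is that adding the earlier readings beside the last one cannot materially widen the intervals with about 462 men per arm.

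**What to change.** In SAP 7.5 (PVR) and 7.3.1 (blood pressure and pulse), add the mean of the available Screening and Run-in readings as a second continuous covariate. Alternatively, enter the two readings separately, which lets the model give less weight to a Screening reading that overlaps washout.

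- Keep the last pre-dose value in the model and as the reference for change from baseline. The descriptive tables then stay as they are. Do not replace it with a three-visit mean.
- In Part 1, use the Hour 0 sitting readings.
- Assign readings by nominal visit, because the Screening and Run-in windows in SAP Table 3 share the date of the first run-in dose. If a Run-in reading has become the baseline because the Baseline reading is missing, leave it out of the second covariate.

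SAP 4.2.2 already provides for additional covariates. The cost is a few lines of SAP text and one or two derived covariates per parameter, with no new data. The change should be fixed before treatment codes are released; a prespecified supportive analysis would also serve.
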